A. Study Type and Design: This is a crossover study with both PwMS and age and sex-matched neurotypical controls. 30 PwMS and 20 neurotypical controls be randomized into two groups and will participate in two split-belt treadmill training sessions while outfitted with cortical fNIRS and TENS devices on their bilateral tibialis anterior and rectus femoris. The first group will complete split-belt treadmill training with TENS OFF during the first visit and TENS ON during the second visit. The second group will complete split-belt treadmill training with TENS ON during the first visit and TENS OFF during the second visit to control for a learning effect. In between visits there will be a 4-week washout period. Participants will receive TENS only during the 10-minute split-belt adaptation period of the paradigm. During all other periods the TENS will be OFF.

B. Sample size, statistical methods, and power calculation

1. Total number of subjects who will be approached (including screen fails, controls and subject withdrawals) to reach enrollment numbers for the lifetime of the study for this investigator's site: 60
2. Total number of subjects to be enrolled at this site: 50

INSTITUTIONAL REVIEW BOARD NON-EXEMPT PROTOCOL TEMPLATE

3. Brief Description/justification for the proposed sample size in *lay terms*: From our preliminary data we computed a large effect size of 1.01 for change in brain activity in the SMA from baseline walking to split-belt treadmill training. According to our power analysis, to maintain an alpha of 0.05 and a power of 0.8, at least 10 participants per group are needed to detect significant changes in brain activity.
4. Simple randomization will occur (TENS first or TENS second) for both groups (PwMS and neurotypical controls).
5. No masking will occur in this study.

C. Subject Criteria (See Vulnerable Populations appendix 1, if applicable): PwMS and neurotypical controls from ages 18-86. All races and genders are included.

1. Inclusion criteria:

- A diagnosis of relapsing remitting multiple sclerosis OR a neurotypical adult (ages 18-86)
- Not experiencing an active relapse
- Able to stand and walk without an assistive device
- Able to walk for three tenths of a mile without stopping to rest
- MS participants must have a neurologist confirmed diagnosis of relapsing-remitting MS.
- MS participants must be independently ambulatory in the community, expanded disability status scale (EDSS) score < 5 (clinical measure of MS severity).

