- 3 Trained graduate students and the principal investigator will determine whether the subject is able to give consent. People with cognitive impairments and minors will be excluded from this study due failing to meet the inclusion/exclusion criteria.

D. Specific procedures and techniques used throughout the study

1. Laboratory tests
 - **Gait Adaptation.** This will be assessed using inertial sensors and 3-D motion capture. Both use noninvasive markers that are placed on the lower limbs of the participants. Our outcome measures assessing gait adaptation will be step length asymmetry (SLA). Step length is quantified by the anterior-posterior distance between heel markers at leading limb heel strike. Step length asymmetry will be calculated by subtracting the step length of the less affected limb from the step length of the more affected limb for each consecutive step and normalized to participant stride lengths and will be assessed continuously throughout each gait trial. We will use step length asymmetry to identify 1) the adaptation rate during the split-belt adaptation period to assess speed of adaptation between conditions and groups, and 2) adaptation savings, or the difference in adaptation rate between visit 2 and visit 1, to quantify adaptation retention between conditions and groups.

INSTITUTIONAL REVIEW BOARD NON-EXEMPT PROTOCOL TEMPLATE

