- **TENS Protocol.** 30 PwMS and 30 age- and sex- matched controls will be randomized into two groups and complete two split-belt treadmill training sessions identical to Aim 1, while outfitted with cortical fNIRS and TENS devices on their bilateral tibialis anterior and rectus femoris. The first group will complete split-belt treadmill training with TENS OFF during the first visit (these are the participants in Aim 1) and TENS ON during the second visit. The second group will complete split-belt treadmill training with TENS ON during the first visit and TENS OFF during the second visit to control for a learning effect. In between visits there will be a 4-week washout period (Figure 3). Participants will receive TENS only during the 10-minute split-belt adaptation period of the paradigm. During all other periods the TENS will be OFF. We will use an FDA-approved clinical TENS device, the LG-TECELITE Therapy System (LGMedSupply, Cherry Hill, NJ). Stimulation will consist of bursting biphasic pulses delivered with electrode pairs (2 in. \times 4 in. pads) placed on the skin over the

INSTITUTIONAL REVIEW BOARD NON-EXEMPT PROTOCOL TEMPLATE

stimulated muscles. The stimulus frequency will be set at 5 Hz with a seven pulses of 0.15 ms based on recent evidence suggesting that bursting TENS is most effective for improving walking performance and limits nerve accommodation to the stimulation. The amplitude of the TENS stimulation will be individualized for each participant in accordance with their specific motor threshold. The TENS amplitude will be slowly increased at 1 mA increments on each individual muscle until non-voluntary muscle contractions can be seen or felt by the investigator, then the amplitude will be set to 2 mA below the motor threshold for each muscle and limb during the split-belt adaptation period. Additionally, we are choosing to outfit TENS on the tibialis anterior and rectus femoris due to previous studies successfully improving gait performance in PwMS using these stimulation locations (Figure 3).

[figure not shown]

Figure 3. (Left) Study design schematic including randomization and TENS condition at each visit. (Right) Example of TENS electrode placement on the bilateral tibialis anterior and rectus femoris.

- **Clinical Assessments**

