- C. Statistical Analysis Plan:** In this crossover design, PwMS and healthy control participants will be pseudo-randomized to begin in either the TENS First or TENS Second condition. Randomization will be performed using a random number generator and will be counterbalanced across age, sex, and fast limb to ensure group balance. A predefined list of participant numbers with corresponding randomized assignments will be generated prior to enrollment. Linear mixed-effects models will be used to identify differences in adaptation and fNIRS outcomes, with group (PwMS vs. healthy controls), visit (Visit 1 vs. Visit 2), and TENS condition (TENS ON vs. TENS OFF), along with their interactions, as fixed effects, and participant number as a random effect. Assumptions of linearity, normality of residuals, and homoscedasticity will be tested for each model. Following model creation, a repeated measures ANOVA will be performed for each adaptation outcome (adaptation rate and adaptation savings) and for cortical activation (HbO beta). Type III ANOVAs with Satterthwaite's method for degrees of freedom estimation will be used for all analyses. Post-hoc comparisons will be conducted using estimated marginal means (EMM) to further investigate significant main effects and interactions. P-values will be corrected using the Benjamini–Hochberg false discovery rate within each outcome and group when applicable. Cohen's d will be calculated to quantify effect sizes. Separate regression models will be conducted to assess the influence of demographic covariates on primary outcome models. All statistical analyses will be conducted using the lme4 and emmeans packages within R and were two-tailed with an alpha threshold set at 0.05.

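### Comparing adaptation savings between TENS conditions repeats the TENS test on adaptation rate with the sign reversed, so it cannot show retention

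*Combined protocol and SAP*

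**What the plan says.** Section I.A.2 states two TENS hypotheses: greater symmetry gains with TENS during split-belt training, and better retention of the adaptation. Section III.D.1 assigns retention to one measure: "adaptation savings, or the difference in adaptation rate between visit 2 and visit 1, to quantify adaptation retention between conditions and groups".

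Section II.A allows only two orders. One group has TENS off at visit 1 and on at visit 2. For the other: "The second group will complete split-belt treadmill training with TENS ON during the first visit and TENS OFF during the second visit". The visits are separated: "In between visits there will be a 4-week washout period". Section III.D.2 (TENS Protocol) adds: "Participants will receive TENS only during the 10-minute split-belt adaptation period of the paradigm". That is the period from which III.D.1 takes the adaptation rate.

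Section V.C (Statistical Analysis Plan) describes a linear mixed model with group, visit and TENS condition, "along with their interactions, as fixed effects, and participant number as a random effect". It then says that "a repeated measures ANOVA will be performed for each adaptation outcome (adaptation rate and adaptation savings") and for cortical activation. It gives no separate model for savings. On allocation, II.B says "Simple randomization will occur (TENS first or TENS second) for both groups", while V.C says participants are "pseudo-randomized to begin in either the TENS First or TENS Second condition", with counterbalancing on age, sex and fast limb.

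**The concern.** Savings subtracts the visit 1 rate from the visit 2 rate. No order keeps TENS in the same state at both visits, so every participant's savings contains the immediate TENS effect, added in one order and subtracted in the other. A comparison of savings by TENS condition then mixes what TENS does while it is on with what it leaves behind four weeks later.

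The two hypotheses would in effect be tested with one statistic. If TENS speeds adaptation, the savings result is pushed towards worse retention for those who had TENS first. If savings is instead labelled by the visit 2 TENS state, the sign flips and the immediate effect looks like a retention benefit. Separately, savings has one value per person and no visit level, so the model named for it has nothing to fit.

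**Working it through.** **1. The plan's own figure.** Section II.B gives at least 10 per group for an effect size of 1.01, alpha 0.05 and power 0.8. A two-sided paired t-test gives power 0.811 at n = 10 and 0.756 at n = 9, so 10 reproduces. It concerns SMA activity and says nothing about savings.

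**2. Cell means for adaptation rate** (larger = faster; III.D.1 ties rate to speed of adaptation). Let π be the visit effect, τ the immediate TENS effect, and λ the extra visit 2 rate from having had TENS at visit 1.

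| Order | Visit 1 | Visit 2 | Savings |
|---|---|---|---|
| TENS second (OFF, ON) | μ | μ + π + τ | π + τ |
| TENS first (ON, OFF) | μ + τ | μ + π + λ | π − τ + λ |

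**3. Contrast.** TENS-first minus TENS-second savings = (π − τ + λ) − (π + τ) = λ − 2τ. If the immediate effect differs by visit (τ1, τ2), it is λ − τ1 − τ2.

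**4. Identity with the rate analysis.** The crossover estimate of TENS on rate is half of (π + τ) − (π − τ + λ), that is τ − λ/2. Multiplied by −2 this is λ − 2τ. In simulated complete data with a 17/13 split of orders, the savings contrast and −2 times the mixed-model TENS effect agreed (−1.0877 for both when λ = 0). Across 500 data sets the two t statistics were equal and opposite.

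**5. Size.** The documents give no SD and no TENS effect on rate, so τ and λ are assumed, in SDs of the within-person difference. The standard error is √(2/15) = 0.365 for 30 PwMS split equally, and √(2/25) = 0.283 for all 50 with common effects. Noncentral t, two-sided 0.05, df 28 and 46:

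| τ | λ | Contrast | Significant, 30 PwMS | Significant, all 50 |
|---|---|---|---|---|
| 0.2 | 0 | −0.4 | 18% | 28% |
| 0.3 | 0 | −0.6 | 35% | 55% |
| 0.5 | 0 | −1.0 | 75% | 93% |
| 0.5 | 0.7 | −0.3 | 12% against TENS-first, 0.3% in favour | 18% against, 0.1% in favour |

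The contrast favours TENS-first only if λ exceeds 2τ.

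**6. What the rate model can say about retention.** (V2-OFF − V1-OFF) − (V2-ON − V1-ON) = (π + λ) − (π + τ2 − τ1) = λ + τ1 − τ2, which is λ if τ1 = τ2. This compares the two orders on each participant's two-visit sum, whose SD is √(2(1 + ρ)) outcome SDs. At ρ = 0.5 (assumed) that is 1.732, and the difference SD is √(2 × 0.5) = 1, so the units match step 5. For λ = 0.7:

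- 15 per order: 0.7/(1.732 × 0.365) = 1.107, power 19%.
- 25 per order: 0.7/(1.732 × 0.283) = 1.429, power 29%.

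In outcome-SD units, for ρ from 0.3 to 0.7, power is 21% to 17% and 32% to 26%. Power of 80% needs λ of 1.71 to 1.95, or 1.31 to 1.49. III.D.2 gives 30 controls instead of 20; with 30 per order, power at ρ = 0.5 is 34%. If τ1 = 0.5, τ2 = 0.2 and λ = 0, the term averages 0.30 and is significant in about 7% (15 per order) or 9% (25 per order) of trials instead of 5%.

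**7. Model fit.** With one savings value per participant, visit is constant and TENS state is a relabelling of order. The eight planned fixed-effect columns have rank 4. lme4 rejects the participant random intercept because there are as many levels as observations.

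**8. What survives.** Savings averaged equally over the two orders is [(π + τ) + (π − τ + λ)]/2 = π + λ/2, free of τ. A raw PwMS-control difference is not free of τ if the orders are unbalanced. With PwMS 12 first and 18 second, and controls 12 first and 8 second, it shifts by τ × [(18 − 12)/30 − (8 − 12)/20] = 0.4τ. Under simple 1:1 randomization of 30 and 20, a shift of at least 0.4τ occurs in 18.5% of allocations.

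**The case against.** The algebra is not in dispute. The strongest counter-arguments are these.

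- **Order is counterbalanced.** That protects the TENS comparison of rate from a visit effect. It does not help here, because order is itself the contrast.
- **The retention term is already in the model.** V.C includes all interactions, so visit × TENS on rate will be estimated. True, but nothing designates it as the retention test; III.D.1 gives that role to savings.
- **The model fault depends on a literal reading.** Savings could be read as the visit contrast of the rate model. That is a sensible repair and is used in the fix, but V.C names savings as an outcome in its own right.
- **The factor −2 is exact only for the crossover estimate, and only with complete data.** This stands. For the pure immediate effect the contrast is λ − 2τ, so it responds to λ but cannot isolate it. A mixed model for rate would also use participants with visit 1 only.
- **The allocation figure assumes simple randomization.** This stands: the 18.5% applies to II.B, and the counterbalancing in V.C would lower it. The main argument does not need it.
- **Every effect size is assumed.** True, hence the range. With the two groups weighted equally (cells of 15, 15, 10 and 10), the all-50 figures become about 27%, 53% and 92%, which changes nothing of substance.
- **The direction of rate is not fully specified.** III.D.1 gives no formula. If rate were coded so that smaller means faster, the signs here would reverse; the confounding would remain.

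**Conclusion.** The concern holds, and the text should be changed before analysis. Compared between TENS conditions, savings adds nothing to the rate result and can return a significant finding in the wrong direction for the retention hypothesis. With no retention effect, that happens in roughly 18% to 75% of trials with 30 PwMS, or 28% to 93% with all 50, for τ from 0.2 to 0.5. The confounding follows from the two orders and the timing of TENS alone. The percentages rest on assumed τ and λ, equal splits by order and complete data. The damage is confined to TENS-related retention: the rate and fNIRS analyses are unaffected. Order-averaged savings and its PwMS-control comparison remain usable if the immediate TENS effect is similar at both visits and in both groups.

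**What to change.** 1. In III.D.1 and V.C, remove savings from the TENS-condition comparisons and from the repeated-measures model. Analyse it with one row per participant (group, order, group × order, no random effect), weighting the two orders equally. Equivalently, take it from the visit and group × visit effects of the rate model. Interpret only the order-averaged results.
2. If TENS-related retention at four weeks is to be tested, name the visit × TENS term of the rate model. Define it as (V2-OFF − V1-OFF) − (V2-ON − V1-ON), so that positive favours retention after TENS when larger rate means faster. With ON = 1 and visit 2 = 1 the model coefficient has the opposite sign. State that it is a between-participant comparison, aliased with order, and equal to λ only if the immediate TENS effect is the same at both visits. Report it with a confidence interval as exploratory and low-powered.
3. State how adaptation rate is computed and which direction means faster.
4. Clarify whether the washout refers to residual TENS effects only, since savings depends on learning that persists across it.
5. Optionally, report early-deadaptation step length asymmetry relative to the same visit's tied-belt baseline, ON versus OFF visits, as a supplementary within-session outcome. It also reflects how much adaptation was achieved and is not savings.

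The cost is SAP and outcome wording; no new data are needed. The downside must be stated openly: this design leaves no well-powered test of TENS on four-week retention, and the one available rests on an equal-effect assumption that the data cannot check.

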- **Cortical Activation via fNIRS.** All fNIRS data will be acquired using a mobile NIRS Sport2 device (NIRx Medical Technologies, nirx.net), which will be secured to participants' backs using backpack-like straps and buckles. This head probe was designed to measure regions of interest (ROI) that were established a priori. The Juelich atlas within the fNIRS Optodes Location Decider (fOLD) toolbox in MATLAB was used to design our optode montage which identifies channel locations above superficial components of the frontal, motor, and sensory regions. Our fNIRS head probe will include 16 sources and 15 detectors which will create 48 channels over the designated ROIs (Figure 1). Additionally, eight short-separator detectors will be used to measure scalp perfusion. All fNIRS data will be acquired and streamed to a laptop using Aurora software v.2021.9 (NIRx Medical Technologies, nirx.net/aurora). Raw fNIRS data will be processed using a commercial software tool, Satori v.1.8 by Brain Innovation (NIRx Medical Technologies, nirx.net/satori) to perform pre-processing steps, such as motion artifact removal, physiological noise detection, and channel selection and removal. Following, the raw light intensity data will be converted to optical density values and then converted to oxygenated hemoglobin (HbO), deoxygenated hemoglobin and total hemoglobin values using the Modified Beer-Lambert Law automatically through Satori software. The HbO beta values calculated from general linear models will be used as a proxy for cortical activity, and we will measure changes in HbO beta between each protocol period described in Figure 2B.

[figure not shown]

Figure 1. Optode montage (16x15) created using Brodmann atlas within fOLD to allow measurement of cortical hemodynamics for premotor, sensorimotor, and posterior parietal regions. Each red circle indicates a source optode, each blue circle represents a detector optode, and each purple connecting line represents a unique channel.

2. Study Procedures:

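### The TENS test on HbO beta does not define its outcome and, on either reading, leaves out the same visit's TENS-free tied-belt beta, which would sharpen the ON-OFF contrast

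*Combined protocol and SAP*

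**What the plan says.** Section III.D.1 (Cortical Activation via fNIRS) takes the HbO beta as the proxy for cortical activity and adds that "we will measure changes in HbO beta between each protocol period described in Figure 2B". The Figure 2 caption in III.D.2 gives the order of periods as baseline (tied-belt), adaptation (split-belt) and deadaptation, with two 30-second blocks averaged in each.

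Section II.A and the TENS Protocol in III.D.2 confine stimulation to the split-belt adaptation period: "During all other periods the TENS will be OFF". Participants wear fNIRS at both sessions. Each visit therefore supplies a tied-belt beta measured before that visit's stimulation and with TENS off.

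Section V.C specifies one linear mixed model for the adaptation and fNIRS outcomes, with group, visit and TENS condition, "along with their interactions, as fixed effects, and participant number as a random effect". It names the fNIRS outcome only as HbO beta. It has no period term and no tied-belt covariate. The only covariates mentioned are demographic ones, in separate regressions.

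**The concern.** Two things are missing from V.C for the TENS test on HbO. The first is the dependent variable. The sentence in III.D.1 suggests a between-period change, and V.C read literally suggests a level. The second is the baseline of the same visit. If the outcome is the split-belt beta, the tied-belt beta is not used at all. If it is the change, the tied-belt beta is subtracted with a fixed weight of 1, which brings in all of its noise. Adding a period factor to the model would not help, because its period-by-TENS term is the same difference of differences as the change score.

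The participant random effect does not fill the gap. It removes stable differences between people, not variation specific to a visit, such as that day's signal quality.

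What is at stake is the width of the interval for the TENS effect on cortical activation, and for its comparison between groups, in a small trial where each beta rests on two 30-second blocks. Leaving the form of the outcome open also allows it to be chosen after the data are seen.

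**Working it through.** **The plan's own figure.** Section II.B.3 reports: "From our preliminary data we computed a large effect size of 1.01 for change in brain activity in the SMA from baseline walking". It then states that "to maintain an alpha of 0.05 and a power of 0.8, at least 10 participants per group are needed". V.C describes the tests as "two-tailed with an alpha threshold set at 0.05". A two-sided paired t-test with d = 1.01 has power 0.756 at n = 9 and 0.811 at n = 10, so the stated 10 reproduces. It concerns baseline walking against split-belt walking and gives no power for TENS ON against OFF.

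**Inputs for the TENS contrast.** Let S and T be a participant's ON-OFF differences in split-belt and tied-belt beta, and r their correlation. Neither r nor the variances are in the documents. I assume equal variances, set to 1, and show a range of r. The relevant r concerns differences between visits, because each participant is compared with himself or herself.

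**Variance of the ON-OFF contrast, relative to split-belt beta alone.**
- Change score: Var(S - T) = 2(1 - r)
- Split-belt beta alone: Var(S) = 1
- Tied-belt covariate with estimated slope: 1 - r²

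The adjusted/change ratio is (1 - r²) / [2(1 - r)] = (1 + r)/2. The adjusted/level ratio is 1 - r².

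| r | change | level | adjusted | adjusted/change | adjusted/level |
|---|---|---|---|---|---|
| 0 | 2.00 | 1 | 1.00 | 0.50 | 1.00 |
| 0.3 | 1.40 | 1 | 0.91 | 0.65 | 0.91 |
| 0.5 | 1.00 | 1 | 0.75 | 0.75 | 0.75 |
| 0.7 | 0.60 | 1 | 0.51 | 0.85 | 0.51 |
| 0.9 | 0.20 | 1 | 0.19 | 0.95 | 0.19 |

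Below r = 0.5 the change score is less precise than ignoring the tied-belt beta altogether.

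**Unequal variances.** The change score's excess variance over the adjusted contrast is (SD_tied - r × SD_split)², and the level's excess is r² × SD_split². Neither can be negative, so the ordering does not depend on the equal-variance assumption.

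**Small-sample penalty.** With n = 30, estimating the slope inflates the adjusted variance by about 1 + 1/26 = 1.038. At r = 0.5 the ratio moves from 0.75 to 0.78. Allowing for this and the lost degree of freedom (27 against 28), an effect with 80% power under adjustment in 30 PwMS has:

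| r | change score | split-belt beta alone |
|---|---|---|
| 0.3 | 64% | 78% |
| 0.5 | 70% | 70% |
| 0.7 | 75% | 53% |
| 0.9 | 79.6% | 24% |

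At r = 0 the split-belt beta alone has about 82%, so the covariate then costs about 2 points.

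**All participants.** Section II.A gives "30 PwMS and 20 neurotypical controls be randomized into two groups", whereas the TENS Protocol gives "30 PwMS and 30 age- and sex- matched controls will be randomized into two groups". The two must be reconciled, but the asymptotic ratios do not depend on N. With N = 50 and the penalty included, the adjusted interval is narrower than the change-score interval by 18.5%, 12.4%, 6.8% and 1.4% at r = 0.3, 0.5, 0.7 and 0.9. The change score would need about 76, 66, 58 and 52 participants to match it.

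**Carry-over.** Suppose TENS at visit 1 shifts both betas at visit 2 by L (an assumption). The shift falls on the OFF visit of the ON-first sequence only, so averaging over the two sequences gives an ON-OFF bias of:
- split-belt beta alone: -L/2
- change score: 0, because the shift cancels
- adjusted: -L/2 + rL/2 = -(1 - r)L/2, in size 0.35L, 0.25L and 0.15L at r = 0.3, 0.5 and 0.7

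**The case against.** The strongest reply is that no text ties the TENS test to the split-minus-tied change. A reader might infer that from III.D.1, but the Figure 2 caption links the between-period comparison to differences in activation between periods, which serves the split-versus-tied hypothesis in I.A.2. V.C names only HbO beta. This stands: the documents support an undefined outcome and an unused baseline, not a commitment to raw change scores.

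A reader might also conclude that the trial uses its 30 PwMS as if they were 19.5 (30 × 0.65). That is one value of an unstated correlation under one of two readings. At r = 0.9 the interval gain over the change score is about 1%, and at r = 0 there is no gain over the split-belt beta alone.

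The tied-belt beta at visit 2 follows the first session, in a trial that expects adaptation to be retained between visits. Adjustment therefore relies on the 4-week washout, and the change score withstands an equal persistent shift better. This also stands and shapes the fix. It does not defend the split-belt beta alone, which is the most exposed of the three.

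Finally, the TENS hypothesis in I.A.2 concerns gait symmetry and retention. TENS on HbO is a planned analysis without a directional hypothesis or power target. That limits the priority of the point but does not answer it.

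**Conclusion.** The point holds as a modest matter of efficiency and specification. V.C leaves the HbO outcome for the TENS test undefined and, on either reading, does not adjust for a pre-stimulation measurement that the trial already collects. Apart from the small cost of estimating a slope, adjustment is at least as precise as either alternative. The gain is largest over the change score when r is low and over the split-belt beta alone when r is high. Its actual size cannot be fixed from the documents, because it depends on r.

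A reader might infer that the planned TENS estimate is biased. The documents do not support that: TENS order is randomised, and without carry-over all three forms estimate the ON-OFF effect without bias. What is lost is precision. The point concerns HbO only, not step length asymmetry.

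**What to change.** In V.C, for each region's TENS test:

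- Name the split-belt HbO beta as the outcome.
- Keep group, visit, TENS and their interactions, with participant as random effect.
- Add the same visit's tied-belt HbO beta as a deviation from the participant's mean, with that mean as a second term, so that within-person and between-person slopes are not mixed. Use the tied-belt period before adaptation, not deadaptation, which follows stimulation.
- If a difference form is preferred, regress the ON-OFF difference in split-belt beta on sequence, group and the ON-OFF difference in tied-belt beta. The group term is needed to estimate group-by-TENS.
- Keep the split-minus-tied change for the split-versus-tied hypothesis, and report it as a sensitivity analysis for TENS because of the washout.
- Do not use the adjusted model for the non-randomised main effect of PwMS against controls.

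The cost is a few sentences in the SAP and one or two model terms, with no new data. If r is near 0, about 2 points of power are lost against the split-belt beta alone. The adjusted estimate also relies on the washout. The choice should be fixed before the HbO data are analysed by TENS condition.
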